# Adaptive Staged SBRT for Spinal Metastases

## SCHEMA

Sample size: 15 patients

## Abbreviations

ACRIN	American College of Radiology Imaging Network
AE	Adverse Event
AJCC	American Joint Committee on Cancer
ANC	Absolute neutrophil count
AUC	Area under the curve
BID	Twice daily
BSA	Body surface area
chemoRT	Chemoradiotherapy
CT	Computed tomography
CTCAE	Common Toxicity Criteria for Adverse Events
CTV	Clinical Target Volume
DFS	Disease-free survival
ECOG	Eastern Cooperative Oncology Group
EQD2	Equivalent dose in 2-Gy fractions
Fx	Fractions
FDG	Fludeoxyglucose
GFR	Glomerular filtration rate
GTV	Gross tumor volume
Gy	Gray
IMRT	Intensity modulated radiotherapy
IV	Intravenous
LA-NSCLC	Locally-advanced non-small cell lung cancer
LD	Longest diameter
LLN	Lower limit of normal
LRC	Locoregional control
MRI	Magnetic Resonance Imaging
MESCC	Metastatic Epidural Spinal Cord Compression
OS	Overall survival

PET	Positron emission tomography
PHI	Protected health information
PI	Principal investigator
PO	By mouth
PTV	Planning target volume
RECIST	Response Evaluation Criteria in Solid Tumors
RT	Radiotherapy
RTOG	Radiotherapy Oncology Group
Rx	Prescription
SAE	Serious adverse event
SBRT	Stereotactic Body Radiation Therapy
SUV	Standardized uptake value
ULN	Upper limit of normal
VMAT	Volumetric modulated arc therapy

## 1.0 OBJECTIVES

### 1.1 Primary Objective

To assess the feasibility of single-fraction radiotherapy to provide a short-interval treatment response in patients with MESCC, such that radiographic decompression is achieved, or additional stereotactic radiotherapy to full therapeutic doses can be delivered while respecting spinal cord constraints, based on the following metrics:

- Shortest distance between gross disease and the spinal cord before and after treatment
- Epidural tumor volume before and after treatment
- Extent of epidural compression before and after treatment

### 1.2 Secondary Objectives

To evaluate pain control using the Numerical Rating Pain Scale (NRPS) before and after treatment

To evaluate patient quality of life using the Functional Assessment of Cancer Therapy-General (FACT-G) before and after treatment

To evaluate functional outcomes using ambulation score and standardized neurologic exams before and after treatment

## 2.0 BACKGROUND

### 2.1 Spinal Cord Compression

Metastatic epidural spinal cord compression (MESCC) is a relatively rare but serious complication of cancer occurring in approximately 5% of diagnosed patients (and can be the presenting symptom in up to 20% of undiagnosed cases). It is a medical emergency, which if not addressed, can lead to permanent neurologic deficits including paraplegia. Although patients with this presentation often do poorly (median survival is estimated at between 3-6 months), there are prognostic indicators of improved outcomes including the preservation of ambulation ability, radiosensitive tumor histology, low systemic extent of disease, and single involved region of the spine [1].

Prompt diagnosis and treatment using a multidisciplinary approach has now become the standard of care. Diagnosis is aided by clinical suspicion based on presenting symptoms, with the most common including back pain, motor deficits, sensory deficits and autonomic dysfunction. Approximately 60% of patients remain ambulatory at presentation [2]. Diagnosis is confirmed radiographically with MRI being the current method of choice (sensitivity and specificity of up to approximately 93% and 98% respectively) [3].

First line therapy for MESCC begins with corticosteroids to reduce edema and provide cytoreductive effects on some sensitive histologies [4]. Until recently, the standard of care for patients was conventional fractionated radiotherapy delivered on an emergent basis. However, a prospective randomized study in 2005 by Patchell et al demonstrated that immediate surgical decompression for a subset of patients followed by adjuvant radiation conferred a number of benefits when compared to radiation therapy alone [5]. Patients preserved the ability to ambulate (84% vs. 57%, p=0.001) and more regained this ability (10 patients vs. 3 patients). Furthermore, those patients undergoing surgery had improved survival times (median 126 days vs. 100 days, p=0.003). The key conclusion from this study was that when used judiciously on a carefully selected cohort of patients, surgical decompression can provide a viable alternative to definitive radiotherapy. These criteria include a non-radiosensitive or unknown primary histology, single area of compression, symptoms present no longer than 48 hours, or relapsed or progression of disease while receiving radiotherapy [1]. It is estimated that 10-15% of patients are appropriate candidates for surgery [2].

For the majority of patients that do not meet the aforementioned criteria or who are poor surgical candidates due to medical comorbidities or other factors, the correct treatment approach is an open question. Definitive radiotherapy remains the standard of care with or without corticosteroids, however there has been no clear demonstration of the effectiveness of conventional treatment for improving neurologic function in patients with MESCC, among several tested dosing regimens [2]. In this pilot study, we plan to evaluate the use of staged high-dose radiotherapy for patients with MESCC, to determine if a treatment response can be observed within a short enough interval to improve symptoms or provide additional radiotherapy safely. We will utilize SBRT where possible as this technique has shown promise in providing disease and symptomatic control to date.

## 2.2 Conventional Radiotherapy

Conventional radiotherapy has historically been the standard of care and remains the most common treatment of MESCC [2]. There have been several randomized trials regarding the optimal dosing regimen in these patients, however none has been found to be significantly effective in improving functional outcomes.

An early example analyzed 276 patients with MESCC comparing two hypofractionated regimens; sequential single-fraction dosing (8 Gy x 2 on days 1 and 8) vs. a split-course regimen (5 Gy x 3, 4-day treatment break, followed by 3 Gy x 5). They found no difference in pain control or post-treatment motor function, with ambulation preserved in approximately 70% in both groups [6]. A larger retrospective comparison from the same year reviewed 1,304 patients comparing five distinct regimens (8 Gy x 1, 4 Gy x 5, 3 Gy x 10, 2.5 Gy x 15, and 2 Gy x 20), and also found no difference in functional outcomes, however noted that local control was improved in the longer courses. Notably, a multivariate analysis identified several factors aside from the treatment regimen that influenced functional outcomes, including age, performance status, tumor histology, number of spinal cord lesions, ambulatory status and interval to treatment [7].

These results were further corroborated by a non-randomized prospective trial including 265 patients with MESCC, comparing a short-course regimen (8 Gy x 1 or 4 Gy x 5) to a long-course (3 Gy x 10, 2.5 Gy x 15, or 2 Gy x 20). The authors found that the radiation schedule had no significant impact on functional outcomes based on univariate analysis (performance status, tumor type, number of vertebrae involved, ambulatory status prior to treatment, and time to symptoms were all significant), though long-courses were associated with improved local control [8]. A systematic review and clinical practice guideline recently recommended that for non-surgical patients, those with poor prognoses should receive 8 Gy x 1, whereas those with more favorable prognoses should be treated with 3 Gy x 10 [4]. It should be reiterated that improvement of motor function was observed in only 28% of patients after shortcourse radiotherapy and in 29% of patients after longercourse radiotherapy, indicating neither is effective for this purpose. Further progression of motor deficits was prevented in 56% and 55% of patients, respectively.

Most recently, another prospective randomized trial comparing 10 Gy x 1 vs. 4 Gy x 5 for patients with MESCC again found both groups performed similarly without a noted improvement in neurologic outcomes [ASTRO 2014]. Improvement in mobility status was even less impressive, occurring in only 10.5% of patients on each arm while improvement in bladder control occurred in 2.6 to 10.5% of patients. Although the 10 Gy arm was not inferior to the 20 Gy arm, this study again showed that conventional definitive radiotherapy had a poor vital and functional prognosis overall.

Currently 10 Gy x 1 using conventional techniques remains an option based on existing clinical data. However, there is clearly a need for a more effective treatment for patients with MESCC who cannot undergo surgery.

## 2.3 SBRT for Spinal Cord Compression

Within the last 10 years, the use of stereotactic body radiation therapy (SBRT) has shown increasing promise in treating spine metastases. A number of retrospective and prospective studies have demonstrated effective local and symptomatic control.

A small retrospective series from Yamada et al initially demonstrated that stereotactic treatment or retreatment of paraspinal lesions up to 70 Gy could be achieved safely using non-invasive body frames. 35 patients underwent treatment with 90% reporting palliation of pain or parasthesias with local control rates of 75-81% [9]. Notably there were no cases of radiation induced myelopathy indicating high-dose per fraction was possible while respecting spinal cord constraints. A larger phase I-II study of spine SBRT then reported on treatment of 63 patients (74 metastatic lesions) with 27-30 Gy in 3-6 fractions. Similarly, they noted 1-year local control rates of 84% [10]. A much larger cohort of 500 patients were prospectively followed by Gertszen et al after receiving single fraction doses of 12.5 or 25 Gy. Long-term pain control was consistent with previous findings of 86%, with local control reported at 90%. Further, 84% of patients with a progressive deficit reported some clinical improvement [11].

Although these findings and others support the use of SBRT for local and symptomatic control for spinal metastases, patients with MESCC present a unique problem of the tumor abutting the thecal sac and cord directly, potentially limiting its application while respecting constraints on the spinal cord dose. In these cases, a therapeutic dose of 16-24 Gy in 1-3 fractions often cannot safely be delivered.

More recently, a prospective clinical trial reported on the effectiveness of SBRT for patients with MESCC, as measured by the reduction of epidural tumor volume and improvement in thecal sac patency. They enrolled 62 patients with MESCC who were treated with 14-20 Gy in a single fraction. The results demonstrated a 64% reduction of the epidural tumor volume at 2 months following treatment, with 80% of the patients also showing improvement in thecal sac patency. Notably, however, 16% of these patients had neurologic progression (9/62 patients). Of these 9 patients, 5 had decompressive surgery thereafter in which 2 showed necrosis, 2 died from intraoperative complications and 1 had tumor progression [12]. This trial indicated that a radiographic response can be observed rapidly, however there is clearly a risk of neurological toxicity from delivering single doses of 14 Gy or higher to tumors abutting the spinal cord.

Previous studies have estimated spinal cord constraints ranging from 10-14 Gy for single fraction SBRT treatments [10, 13, 14]. RTOG 0631, an ongoing prospective randomized trial which investigated the use of SBRT for palliation of spine metastases (16 Gy SBRT vs. 8 Gy x 1 conventional), applied these constraints using 10 Gy to 10% of the spinal cord (cross sectionally) to a maximum of 6mm above and below the target volume, and max dose of 14 Gy. However, patients are excluded if there was frank epidural compression within 3 mm of the spinal cord.

Based on the above findings, we are proposing a trial for patients with inoperable MESCC utilizing adaptive planning and a staged application of radiotherapy. Such an approach can potentially deliver therapeutic doses to the tumor while respecting the established spinal cord constraints. We hypothesize that a single fraction of treatment may induce a short-interval radiographic response (within approximately 2-3 weeks), which can then be used to plan an additional treatment if needed. The response may

also allow us to achieve therapeutic dose levels by reducing the volume of overlap with the spinal cord. We will also observe the radiographic response from high-dose single fraction regimens if decompression can be achieved in this fashion.

## 3.0 PATIENT ELIGIBILITY

Patients will be recruited via physician referral. Each of the criteria in the checklist that follows must be met in order for a patient to be considered eligible for this study. The eligibility checklist must be completed on the case report form and maintained in each patient's chart.

### 3.1 Inclusion Criteria

Localized spine metastasis from the C1 to L5 levels with documented epidural extension or spinal cord compression by a diagnostic imaging study (MRI, diagnostic CT, or CT myelogram recommended). Site(s) may have a maximal involvement of 3 contiguous vertebral bodies. Patients with other visceral metastasis, and radioresistant tumors (including soft tissue sarcomas, melanomas, and renal cell carcinomas) are eligible.

History/physical examination by the treating physician within 7 days prior to study therapy

Neurological and functional examination within 7 days prior to study therapy by the treating physician (see Appendix D).

Negative serum pregnancy test

Age  $\geq$  18

Diagnostic Imaging (MRI with gadolinium is recommended, other modalities include CT myelogram or diagnostic CT with iodinated contrast) of the involved spine within 21 days prior to initial study therapy to determine the extent of the spine involvement

Numerical Rating Pain Scale within 7 days prior to study therapy; Documentation of the patient's initial pain score is required. Patients taking medication for pain at the time of registration are eligible.

Women of childbearing potential must:

- Have a negative serum or urine pregnancy test within 1 week prior to the start of study therapy
- Agree to utilize an adequate method of contraception throughout treatment and for at least 4 weeks after study therapy is completed
- Be advised of the importance of avoiding pregnancy during trial participation and the potential risks of an unintentional pregnancy.

All patients must sign study specific informed consent prior to study entry or within 1 week of first treatment, provided other criteria were met.

Patients considered for enrollment are strongly recommended to have been discussed at multidisciplinary tumor board with input from surgery, medical oncology and radiation oncology prior to enrollment.

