## 4.0 STUDY DESIGN

### 4.1 General Design

#### *Treatment*

This will be a pilot study assessing the feasibility of staged radiotherapy and adaptive planning on the management of inoperable epidural extension or spinal cord compression (documented by diagnostic imaging). All patients should be started on dexamethasone unless medically contraindicated and dosed per institution guidelines. Initial treatment after evaluation and registration will consist of an initial fraction of 8-24 Gy delivered using a SBRT or 3D conformal approach to the affected region(s). The patients will be re-imaged within 14-21 days by the same modality as diagnosis to assess for radiographic response. If feasible, a second fraction will be delivered at this point per discretion of the treating physician.

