#### *Follow-up*

Patients will be evaluated with a history, physical examination, pain score, and neurologic assessment at each treatment visit by the treating physician, or more frequently as clinically indicated. Interval diagnostic imaging will be completed 14-21 days after initial treatment to assess response. Thereafter, a third set of diagnostic images will be obtained at 8-10 weeks following initial treatment. Patients will be followed thereafter by the treating physician for survival and recurrence as clinically indicated.

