### 4.4 Secondary Endpoints

Pain control: Pain scores as measured by the Numerical Rating Pain Scale (NRPS) estimation

Quality of Life: Scores from Functional Assessment of Cancer Therapy (FACT-G)

Ambulation: Based on ambulation score and standardized neurologic exam (Appendix D)

Progression-free survival: the interval from study registration to date of disease progression or death, censored at the date of data collection

Overall survival: the interval from study registration to death, censored at the date of data collection

Grade  $\geq$  2 radiation-induced lung toxicity, scored using CTCAE, v. 4

Any grade  $\geq$  3 treatment-related toxicity, scored using CTCAE, v. 4

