## 7.0 STATISTICAL CONSIDERATIONS

### 7.1 Data Analysis

This pilot study will yield preliminary data on the primary endpoint of distance between gross disease and spinal cord of at least 3mm. Data from the study will be summarized using standard descriptive statistics; formal hypothesis testing will not be performed. Estimates of the treatment effect and standard error on the number of subjects achieving  $\geq 3$  mm distance will also be used to determine the sample size required for the larger scale study. Therefore, the size of the pilot study should be sufficient to produce reasonably precise estimates of these parameters, where precision is measured by the width of the 95% confidence interval.

The treatment effect will be estimated by  $p$ , the observed proportion of patients achieving at least 3 mm distance from the gross disease and spinal cord. Confidence intervals for the true proportion will be computed using Clopper-Pearson exact confidence interval. With 24 subjects and assuming an expected response rate  $p = 50\%$  produces a two-sided 95% confidence interval with a width equal to 58% (i.e.  $21\% \leq p \leq 79\%$  ). The width shows that the response rate will not be lower than 20%. Since this is a feasibility, study no power calculation is done.

Data regarding secondary endpoints will be reported in a descriptive manner.

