## 13.0 APPENDICES

### 13.1 Appendix A – Eligibility Checklist

#### Inclusion Criteria

Must be answered **YES** for eligibility

1. Does the patient have pathologically proven malignancy? **Yes / No**
2. Does the patient have demonstrated metastatic epidural cord compression on diagnostic imaging? **Yes / No**
3. Has the patient been evaluated by neurosurgery or orthopedic surgery and is not proceeding? **Yes / No**
4. Has the patient had an appropriate pre-treatment work-up, including complete history, physical examination and neurologic evaluation? **Yes / No**
5. Does the patient have ECOG Performance Status 0-2? **Yes / No**
6. Is the patient at least 18 years old? **Yes / No**
7. Is either of the following true?:
  - The patient is not a woman of childbearing potential.
  - The patient has undergone negative serum or urine pregnancy test within 72 hours prior to the start of study therapy, agrees to utilize an adequate method of contraception throughout treatment and for at least 4 weeks after study therapy is completed, and has been advised of the importance of avoiding pregnancy during trial participation and the potential risks of an unintentional pregnancy.**Yes / No**
8. Has the patient signed study-specific informed consent? **Yes / No**

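### As written, Section 3.1 allows consent to be signed after the first fraction, which conflicts with treatment following registration and can leave early failures uncounted.

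*Combined protocol and SAP*

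**What the plan says.** The consent criterion in Section 3.1 (Inclusion Criteria) reads: "All patients must sign study specific informed consent prior to study entry or within 1 week of first treatment, provided other criteria were met".

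The text that bears on it:

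- Section 3.0 (Patient Eligibility): "Each of the criteria in the checklist that follows must be met in order for a patient to be considered eligible for this study".
- Appendix A, inclusion item 8, which must be answered yes: "Has the patient signed study-specific informed consent". The item has no date and no time point.
- Section 4.1 (Treatment): "Initial treatment after evaluation and registration will consist of an initial fraction of 8-24 Gy". Registration therefore comes first.
- Section 4.1 (Follow-up): "Interval diagnostic imaging will be completed 14-21 days after initial treatment to assess response".
- Section 4.4 defines overall survival as "the interval from study registration to death, censored at the date of data collection". Progression-free survival has the same starting point.
- Section 7.1 estimates the treatment effect by "the observed proportion of patients achieving at least 3 mm distance from the gross disease and spinal cord". It does not say which patients form the denominator or how a patient without an interval scan is counted.

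The Schema gives a sample size of 15. Section 7.1 instead writes "With 24 subjects and assuming an expected response rate" of 50%.

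**The concern.** The consent sentence offers two routes joined by *or*: before entry, or inside a one-week window around first treatment. If the second route extends past the first fraction, a patient can receive study treatment and be enrolled afterwards. Two things follow.

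First, entry can depend on how the patient fared in the first days. Patients who die, deteriorate neurologically, go to surgery or become unable to sign would have been treated but never counted. The loss runs in one direction: it removes early failures and early toxicity. The response proportion is meant to size a larger study, and the monitoring committee reviews events from enrolled patients, so both uses are affected. PFS and OS would describe only patients who survived to consent.

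Second, study treatment could precede consent. Section 8.1 requires patients to be fully informed about a trial they volunteer for, and a signature after the first fraction does not achieve that for that fraction. This problem exists whatever the size of any bias.

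**Working it through.** **Which way the window points.** Section 3.1 sets five other assessment windows: history and physical, neurologic examination, imaging, pain score and pregnancy test. Each is expressly placed *prior* to study therapy. The consent window alone omits that word. Treatment follows registration under Section 4.1, so the first route (before entry) already lies before treatment. If the second route meant only the week before treatment, it would add almost nothing. The closing proviso, in the past tense, also suits a look back at a patient already treated.

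**Where the conflict lies.** Take a patient who signs on day 5.

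- Section 3.1 accepts the patient.
- Under Section 3.0 and Appendix A the patient was not yet eligible on day 1, because a required criterion was unmet.
- Under Section 4.1 the first fraction follows registration. So either an ineligible patient was registered or treatment came before registration.

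The conflict needs these sections together. Item 8 alone does not create it.

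**The plan's own figure.** The only precision figure is the exact 95% interval for 24 subjects at 50%, given as 21% to 79% (width 58%). Clopper-Pearson for 12/24 gives 29.1% to 70.9% (width 41.8%). The stated interval is that of 6/12, 21.1% to 78.9% (width 57.8%). This is a separate error, and nothing here depends on it.

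**Illustration of size.** Inputs: median survival of 3-6 months (Section 2.1); n = 15 (Schema) or 24 (Section 7.1). Assumptions: constant hazard, and every patient using the late route.

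P(death within 7 days) = 1 − 0.5^(7/m), with m the median in days:

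- 3 months: 1 − 0.5^(7/91.3) = 5.2%
- 6 months: 1 − 0.5^(7/182.6) = 2.6%

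| Treated | Expected deaths by day 7 | Chance of at least one, 1 − (1 − P)^n |
|---|---|---|
| 15 | 0.4 to 0.8 | 33% to 55% |
| 24 | 0.6 to 1.2 | 47% to 72% |

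The expected count scales with the share s who consent late. At s = 50% it is 0.2 to 0.4 of 15, or 0.3 to 0.6 of 24. At s = 0 it is zero.

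Effect on the observed proportion when k non-responders are never enrolled, x/(n − k):

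| | k = 0 | k = 1 | k = 2 |
|---|---|---|---|
| x = 7, n = 15 | 46.7% | 7/14 = 50.0% | 7/13 = 53.8% |
| x = 12, n = 24 | 50.0% | 12/23 = 52.2% | 12/22 = 54.5% |

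The 12 is the plan's assumed 50% of 24. The 7 is one of the two whole numbers nearest to 50% of 15.

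**The case against.** The strongest reply is that this is one loosely drafted sentence in a descriptive pilot with no hypothesis test. The window may have been meant as the week before treatment, and the general requirements of Section 8.1 stand in any case. Section 2.1 calls the condition an emergency, and Section 2 describes single fractions of 8 or 10 Gy as existing options, so some first fractions may amount to usual care. A shift of a few points is small beside the exact interval for 7/15 (21.3% to 73.4%).

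Part of this stands. The intended direction cannot be proved, and consent pages were not available for this review, so other text on timing may exist. The usual-care argument is not the protocol's stated rationale and does not cover the higher doses in the 8-24 Gy range. The interval describes sampling error only, so a directional loss of failures lies outside it.

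A reader might also infer four stronger points that the documents do not support:

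- *That the radiographic result decides who enters.* Response is read at day 14-21, after the week has closed. Only early clinical course can select patients.
- *That Appendix A item 8 contradicts Section 3.1 by itself.* It has no time point, and a patient signing on day 5 can still answer yes.
- *That the FACT-G slot at day -7 to -1 contradicts late consent.* The calendar sets when the questionnaire is measured, and FACT-G is not an inclusion criterion. A late consenter may lack a baseline, but that is a missing-data matter.
- *That late registration adds guaranteed survival time to PFS and OS.* Days before registration are not counted. What remains is selection of patients who survived to consent.

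The size figures also need care. The 3-6 month median is for the condition in general, while Appendix A restricts entry to ECOG 0-2. Patients who die by day 7 have no interval scan, so under Section 7.1 they might leave the denominator even with prior consent. The shift is therefore not due to consent timing alone.

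**Conclusion.** The point holds in a limited form. Section 3.1 permits consent after the first fraction, and this cannot be squared with Section 4.1 read with Section 3.0 and Appendix A. Followed as written, it lets study treatment precede consent and lets early failures and early toxicity go uncounted.

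The statistical size is unknown, because the documents give no share of late consenters. The figures above are an upper-end illustration: each early failure lost adds roughly 2 points to the response proportion at 24 treated and 3 to 4 points at 15. They do not show that any patient has been or will be enrolled this way. The need for an amendment rests on the contradiction and on consent preceding study treatment. The possible bias adds to it but is not needed for it.

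**What to change.** - Amend Section 3.1 so that consent is signed before registration and before the first study fraction. If a window covering the 7 days before first treatment was meant, say so.
- Reconcile Sections 3.0, 3.1 and 4.1 and Appendix A item 8 with that rule, and give item 8 a time point.
- Record the consent and registration dates relative to the first fraction on the case report form. If any patient has already entered under the present sentence, report how many signed after the first fraction.
- In Section 7.1, define the primary denominator as all consented patients who receive the first fraction, and count those without an interval scan as non-responders. Report their number separately, since this rule mixes early death with lack of shrinkage. Amending consent alone would leave this gap open.

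The cost is a few sentences in an amendment and two date fields. The real downside is that some emergently treated patients could not be enrolled. The documents do not allow that number to be estimated.
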